Primary Hypothesis 1: Adjunctive treatment with buprenorphine 4 mg during the first 5 weeks of naltrexone maintenance will improve opioid abstinence and treatment retention, defined as receiving the second XR-NTX injection.

Primary Hypothesis 2: Providing buprenorphine 4 mg daily during gradual 9-day titration of oral naltrexone will improve tolerability and success of XR-NTX induction, defined as receiving the first XR-NTX injection.

Primary Hypothesis 3: Providing buprenorphine 4 mg daily during gradual 9-day titration of oral naltrexone and adjunctive treatment with buprenorphine 4 mg during the first 5 weeks of naltrexone maintenance will significantly improve opioid abstinence and treatment retention, defined as receiving the second XR-NTX injection.

Primary Aim 4: To examine in biofluid-derived extracellular vesicle content for the existence of biomarkers related to naltrexone treatment.

Description of Subject Population

Sample #1

Specify subject population

Adults with current Opioid Use Disorder

Number of completers required to accomplish study aims

15

Projected number of subjects who will be enrolled to obtain required number of completers

30

Age range of subject population

18-60

Gender, Racial and Ethnic Breakdown

Both genders and all ethnic groups are eligible. It is estimated that the sample will be 60% male, 40% female, 50% Caucasian, 30% Hispanic-American, 15% African-American, and 5% other minorities based on data from previous trials.

Description of subject population

Prospective participants must be adult (18 to 60 years of age) and meet criteria for current opioid use disorder by history and urine toxicology. Other substance use diagnoses are not exclusionary since multiple substance abuse is common in this population, and such an exclusion would rule out a large proportion of the population and limit the generalizability of the study. However, physiological dependence on alcohol or sedative-hypnotics with impending withdrawal is exclusionary. Maintenance on methadone or other long-acting agonist (e.g. buprenorphine) or regular use of illicit methadone (> 30 mg per week) is exclusionary. Prospective participants cannot have concurrent psychiatric or medical conditions that would interfere with

participation (e.g. mania, psychosis, suicidality, pregnancy or failure to use adequate contraception).

Recruitment Procedures

Describe settings where recruitment will occur

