Adjuvant medications for Procedure 1 include: Clonidine 0.1 mg QID (MDD=0.4 mg), clonazepam 0.5 mg QID (MDD=2.0 mg), prochlorperazine 10 mg QD, trazodone 100 mg HS, and zolpidem 10 mg HS. Clonidine will be held if blood pressure falls below 90/60 mm Hg at any visit's vitals check. Adjuvant medications will be offered for one week following administration of XR-NTX as needed for persistent withdrawal symptoms.

If opioid use occurs in combination with missed doses of naltrexone, a naloxone challenge will be administered to confirm that the next dose of oral naltrexone will be tolerated; if necessary, an additional day of adjuvant medication only will be given. In patients at risk for greater withdrawal symptoms (e.g.

history of severe withdrawal, more severe dependence (> 6 bags per day), or a strong reaction to the first dose of naltrexone), the procedure may be slowed down by 1 or 2 days. Once a patient has tolerated a first daily dose of naltrexone 25 mg, he/she is eligible to receive XR-NTX 380 mg IM on Day 5.

Procedure 2:

Design

Patients will undergo a modified outpatient buprenorphine-clonidine-naltrexone procedure to initiate treatment with XR-naltrexone (XR-NTX). During a 10-day procedure, oral naltrexone will be very slowly titrated upwards to the full dose of oral naltrexone but buprenorphine will remain at the same dose of 4 mg a day starting on Day 2. At the end of the procedure, participants will receive the injection of XR-NTX, and the second XR-NTX injection will be administered 4 weeks later. No buprenorphine will be given beyond Day 10.

Rationale

We hypothesize that a gradual titration of naltrexone while maintaining stable doses of buprenorphine will allow for a transition from an opioid agonist to an opioid antagonist state with minimal withdrawal severity. Based on our extensive experience administering low-doses of naltrexone we believe that repeated administration of very low-doses of naltrexone with 1-day dosing interval should not precipitate severe withdrawal. Because of the long-duration of receptor binding naltrexone will accumulate at the receptor and over time it will replace the buprenorphine at the receptor.

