This is a variation of the methods described by Resnick et al., (1977) and Hammig et al., (2016). Resnick gave increasing doses of naloxone over 1-2 days to participants who stopped methadone maintenance (and presumably still had methadone present in their brain when naloxone was given). The severity of precipitated withdrawal was decreasing with each subsequent naloxone dose and at the end of the procedure participants had negative naloxone challenge and received oral naltrexone 100 mg. This method was further elaborated by Charney et al., (1982) who administered increasing doses of naltrexone over 4-day period to participants who were maintained on methadone (20-30 mg/d) prior to this procedure.

Hammig described a "Bernese Method" where small doses of buprenorphine are titrated upward while the subject continues taking full agonist (Hammig et al., 2016). While in the Bernese method, opioid agonist is stopped once the therapeutic dose of buprenorphine is reached we will continue administering buprenorphine even after the full blocking doses of naltrexone is reached as it is known that buprenorphine can be safely administered in combination with naltrexone in participants who were first treated with naltrexone.

We have experience (30 participants) administering buprenorphine 8 mg for 1 day followed by a day of washout and increasing doses of naltrexone for 2 days with a full blocking dose of naltrexone reached on day 3

We hypothesize that with a very slow and gradual upwards titration of naltrexone while the participant receives overlapping buprenorphine we will avoid the precipitation of severe withdrawal and will be able to arrive at the blocking dose of naltrexone 25 mg/d followed by an injection of XR-naltrexone.

Study Medications Dosing

On the morning of Day 1, participants will receive 2 mg of buprenorphine, to be followed by a second dose after 1-2 hours. Participants will receive a total of 8mg of buprenorphine on Day 1. Patients will then receive 4mg of buprenorphine on Days 2-10. Beginning on Day 2 participants will receive increasing doses of naltrexone 30 minutes after the dose of buprenorphine 4 mg has been administered, starting with 0.25mg titrating up to 25mg on Day 10 (Day 2:0.25mg; Day 3: 0.5mg; Day 4: 1mg; Day 5: 2mg; Day 6: 3mg; Day 7: 6mg; Day 8: 12mg; Day 9: 25mg; Day 10: 25mg. On Day 10 participants will receive a dose of XR-NTX, and a 2nd dose 4 weeks later. No buprenorphine will be given beyond Day 10.

Procedure 3:

Design

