Procedure 3 is a combination of procedure 1 (BUP 4 mg/d given in combination with XR-NTX) and procedure 2 (slow titration of oral naltrexone while maintaining stable BUP dose).

Rationale

This is a combination of Procedure 1 and 3

Study Medications Dosing

On the morning of Day 1, participants will receive 2 mg of buprenorphine, to be followed by a second dose after 1-2 hours. Participants will receive a total of 8mg of buprenorphine on Day 1. Patients will then receive 4mg of buprenorphine on Days 2-10. Beginning on Day 2 participants will receive increasing doses of naltrexone 30 minutes after the dose of buprenorphine 4mg has been administered, starting with 0.25mg titrating up to 25mg on Day 10 (Day 2:0.25mg; Day 3: 0.5mg; Day 4: 1mg; Day 5: 2mg; Day 6: 3mg; Day 7: 6mg; Day 8: 12mg; Day 9: 25mg; Day 10: 25mg. Participants will receive XR-NTX on Day 10 together with buprenorphine 4mg, and will continue to receive buprenorphine 4mg for 4 weeks until they receive the 2nd XR-NTX dose. Following the second XR-NTX injection, the buprenorphine dose will be decreased in Study Week 5 to 2 mg for 4 days after which it will be stopped.

If a significant withdrawal symptoms emerge during the naltrexone titration, the next dose of naltrexone will be repeated (rather than doubled) and therefore the procedure may be slowed by 1-3 days. Once a patient has tolerated a first daily dose of naltrexone 25 mg, he/she is eligible to receive XR-NTX 380 mg IM.

Adjuvant medications (Procedures 2 & 3)

We believe that there will be less withdrawal symptoms in participants receiving buprenorphine therefore we will use lower standing doses of medications with the option to administer additional doses as needed for breakthrough withdrawal. We will administer Clonidine 0.1 mg BID and clonazepam 0.5 mg BID daily. Additional doses of clonidine 0.1 mg (MDD=0.4 mg), clonazepam 0.5 mg (MDD=2.0 mg), prochlorperazine 10 mg QD, trazodone 100 mg HS, and zolpidem 10 mg HS will be administered as needed. Clonidine will be held if blood pressure falls below 90/60 mm Hg at any visit's vitals check. Adjuvant medications will be offered for one week following administration of XR-NTX as needed for persistent withdrawal symptoms.

Treatment Period

Adherence to oral naltrexone

All doses of buprenorphine and oral naltrexone will be directly observed when possible. If a significant withdrawal symptoms emerge during the naltrexone titration, the next dose of naltrexone will be repeated

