(rather than doubled) and therefore the procedure may be slowed by 1-3 days.

XR-NTX Injections

XR-NTX will be administered on either Day 5 (Procedure 1), or Day 10 (Procedures 2 & 3), as an intramuscular injection (380 mg) in one buttock by one of the research psychiatrists or research nurses of the clinic, who are currently trained and administer XR-NTX in other protocols. All participants will be required to remain at the clinic for 1 hour of observation following the first injection, to monitor vital signs and to observe for any increased withdrawal symptoms or side effects. At the beginning of Week 4 (4 weeks post-XR-NTX injection) participants will receive a second injection of XR-NTX.

Procedures for Missed Doses of XR-NTX

If the patient misses a scheduled second injection and takes an opioid during at least two of the seven days following the date of the scheduled injection, relapse will be suspected, and we will perform a naloxone challenge, if appropriate, using 0.8 mg naloxone, administered intramuscularly. The patient is followed clinically and withdrawal symptoms are assessed over the next hour. If the challenge is negative, the administration of XR-naltrexone will be resumed. If fully positive, the patient will have relapsed as XR-naltrexone may precipitate significant withdrawal so it cannot be resumed. However, because there are blood levels and partial blockade beyond Week 5, vulnerability to relapse may be more gradual, and the instance of mild or equivocal reactions to naloxone challenge more common. In this instance, a second challenge within 72 hours, or escalating doses of oral naltrexone over 3 days will be attempted, and if tolerated, the next injections can be given. Patients who fail two consecutive naloxone challenges are considered to have relapsed and are referred for inpatient detoxification or agonist maintenance, as deemed clinically appropriate and in accordance with the patient's wishes.

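### Procedure 2 ends buprenorphine at Day 10 but lets the naltrexone titration run 1-3 days longer; read literally, a 2- or 3-day delay can put the 12 to 25 mg step after the last buprenorphine dose

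*Protocol*

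**What the plan says.** **Buprenorphine.** Procedure 2, Study Medications Dosing: "Patients will then receive 4mg of buprenorphine on Days 2-10", and then "No buprenorphine will be given beyond Day 10". The Lay Summary and the Procedure 2 Design text set the same stop. None of the three gives an exception for a slowed titration.

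**Naltrexone.** The same dosing section starts at 0.25 mg on Day 2 and ends "Day 6: 3mg; Day 7: 6mg; Day 8: 12mg; Day 9: 25mg; Day 10: 25mg". Each naltrexone dose follows that day's buprenorphine by 30 minutes.

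**Slowing.** If significant withdrawal emerges, "the next dose of naltrexone will be repeated (rather than doubled) and therefore the procedure may be slowed by 1-3 days". The rule stands in the Procedure 3 dosing text and again under Treatment Period, Adherence to oral naltrexone. That section is not limited to one procedure, so the rule reaches Procedure 2. No threshold for significant withdrawal is given.

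**Injection.** The first XR-NTX injection is set at Day 10 in Procedure 2, Study Medications Dosing, and in XR-NTX Injections. The Pregnancy risk section ties the pre-injection urine test to the same day.

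**Hypothesis and outcome.** Primary Hypothesis 2: "Providing buprenorphine 4 mg daily during gradual 9-day titration of oral naltrexone will improve tolerability and success of XR-NTX induction". In the SAP, Study Outcome Measures, the Procedure 2 primary outcome is receipt of the first injection. Sample Size allots 10 participants to each procedure.

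**The concern.** Buprenorphine ends on a numbered day, whereas the titration ends when the dose has been tolerated. The two coincide only if nobody is slowed. Participants are slowed because of withdrawal, so the rules separate in people already known to have significant symptoms.

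Three other parts of the protocol assume that buprenorphine is still present:

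- The Procedure 2 Rationale says that buprenorphine goes on after the full blocking dose of naltrexone has been reached. Under the literal stop, a participant slowed by 2 or 3 days before 25 mg would lose it before that dose.
- The lower standing adjuvant doses in Procedures 2 and 3 are justified by participants being on buprenorphine.
- The withdrawal ratings on induction days are timed from the buprenorphine dose.

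The first 25 mg dose also matters for the outcome. Criteria for Early Discontinuation counts moderate or severe withdrawal in response to 25 mg (COWS 13-36) as dropout. A participant who dropped out there without buprenorphine would be a Procedure 2 failure on the primary outcome, although the combination in Hypothesis 2 was absent at that step. The SAP's Study Analysis reports no extensions, so a reader could not tell failure of the method from failure to deliver it.

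**Working it through.** The documents give no power calculation, so the check is a count of days.

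**Inputs (Procedure 2 dosing section and the slowing rule).** Eight dose levels: 0.25, 0.5, 1, 2, 3, 6, 12 and 25 mg, then a second 25 mg dose. First dose on Day 2, one dose a day. Last buprenorphine on Day 10. Total delay k = 1, 2 or 3 days, each day being one repeated dose.

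**The plan's own figure.** With no repeats, level j falls on Day j + 1, so the first 25 mg (j = 8) is on Day 9 and the second on Day 10. Days 2 to 10 are 9 dosing days, all with buprenorphine. This reproduces the 9-day titration in Hypothesis 2.

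**With repeats.** Level j is first taken on Day j + 1 + (number of repeats at lower levels).

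- First 25 mg: Day 9 + R, where R is the number of repeats below 25 mg. It falls after Day 10 if R ≥ 2.
- First 12 mg: Day 8 + S, where S is the number of repeats at 6 mg or below. It falls after Day 10 only if S = 3.
- First 6 mg: Day 7 + at most 3 = Day 10 at the latest, so it is always covered.

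**All possible placements.** k repeats can be spread over 8 levels in C(k + 7, k) ways.

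| Delay | Nine-dose schedule ends | Patterns | 12 to 25 mg uncovered | 6 to 12 mg also uncovered |
|---|---|---|---|---|
| 1 day | Day 11 | C(8,1) = 8 | 0 | 0 |
| 2 days | Day 12 | C(9,2) = 36 | C(8,2) = 28 | 0 |
| 3 days | Day 13 | C(10,3) = 120 | C(9,3) + C(8,2) = 84 + 28 = 112 | C(8,3) = 56 |

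In the 3-day row, 84 patterns have all repeats below 25 mg, and 28 have two below and one at 25 mg. The 56 have all three repeats at the six levels up to 6 mg. These are counts of possible patterns, not probabilities.

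**Size of the steps.** 25 − 12 = 13 mg is the largest increase in the schedule and 12 − 6 = 6 mg the second largest.

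**The 1-day case.** The first 25 mg falls on Day 10 at the latest, so only the second 25 mg dose, and possibly the injection, moves to Day 11. The sentence making a participant eligible for injection after one tolerated 25 mg dose stands in the Procedure 1 and Procedure 3 texts. If it also governs Procedure 2, the injection could still be given on Day 10.

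**The other reading.** If buprenorphine ends with the procedure, whenever that is, no titration day is uncovered at any delay.

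**Weight in the outcome.** 1/10 = 10 percentage points per participant.

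**The case against.** The strongest reply is that Day 10 is a nominal label for the end of a 10-day procedure. The injection is fixed at Day 10 too, yet a slowed titration can move it. In the Lay Summary the stop serves to contrast Procedure 2 with the four further weeks of buprenorphine in Procedure 3, so it may be meant only to exclude buprenorphine after the injection. The Rationale and the pairing of each naltrexone dose with buprenorphine fit that reading.

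This is plausible, and the documents never speak of a calendar day. But the Procedure 2 Design text places the injection at the end of the procedure and then, in its next dosing statement, stops buprenorphine at Day 10. Staff could reasonably follow either reading, so the reply explains the conflict without resolving it.

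It can also be said that this is an uncontrolled, descriptive pilot with on-site monitoring, 24-hour physician cover and as-needed adjuvants. Those limit the risk to participants. They do not settle which treatment is being evaluated.

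A reader might infer more than the text supports:

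- **That every slowed participant loses buprenorphine at the largest steps.** A 1-day delay leaves no increase uncovered, nor does a longer one with fewer than two repeats below 25 mg. Two uncovered steps need a 3-day delay with all repeats at 6 mg or below.
- **That those affected have the most withdrawal.** The trigger is significant withdrawal; nobody is ranked.
- **That Procedure 3 has the same gap.** The Lay Summary and the Procedure 3 dosing text say that buprenorphine continues until the second injection.
- **That Procedure 1 is equally affected.** Its own text says "the procedure may be slowed down by 1 or 2 days", against 1-3 days in the common section. That is a real but secondary mismatch, and repeating instead of doubling does not suit a titration from 1 mg on Day 3 to 25 mg on Day 5.

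**Conclusion.** The point holds for Procedure 2 in conditional form. The stop at Day 10 and the 1-3 day extension are both stated and are not reconciled. Followed literally, at least two repeats before 25 mg put the largest naltrexone increase on Day 11 or 12 without buprenorphine, contrary to Hypothesis 2 and the Procedure 2 Rationale.

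This rests on three assumptions: Day 10 is counted from the first buprenorphine dose whatever the progress of the titration, the common slowing rule applies to Procedure 2, and each day of delay is one repeated dose. If the sponsor meant Day 10 as the nominal end of the procedure, the gap closes and only the wording needs correction.

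The effect on the primary percentage cannot be estimated, because the documents do not say how many of the 10 participants would be slowed or how an uncovered step would change their chance of injection. The 10 points per participant is the weight of one outcome, not a predicted bias.

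**What to change.** In the protocol, the sponsor should reconcile the Lay Summary and the Procedure 2 Design and dosing texts with the slowing rule in the Procedure 3 dosing and Treatment Period texts. The fixed Day 10 injection statements in Procedure 2, XR-NTX Injections and the Pregnancy section need the same treatment. The end of Procedure 2 buprenorphine, the extendable titration and the injection should share one stated anchor. Which anchor, and what is given on extension days, is the sponsor's clinical decision; no rule is proposed here.

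In the SAP, Study Analysis, add one descriptive item: how many participants were extended, by how many days, and whether any naltrexone increase was taken without buprenorphine.

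The cost is a short protocol amendment, one SAP line and a variable length of study-drug supply for extended participants. No additional participants are needed.

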### **Study Objectives and Endpoints**

The primary objective of this pilot open-label study is to evaluate three new outpatient pharmacological procedures to facilitate transition onto a long-acting, injectable form of naltrexone 380 mg (XR-NTX).

The primary aim is to test the feasibility, safety, and effectiveness of the new methods to improve tolerability of naltrexone induction and reducing attrition during detoxification and the first month of naltrexone treatment.

The primary endpoint is the receipt of the two injections of XR-naltrexone given first after completion of the detoxification and induction procedure and the second administered 4 weeks later.

### **Study Participants and Design**

Participants in the study are individuals with opioid use disorder (OUD) who are actively using opioids and are seeking treatment with naltrexone as a relapse-prevention intervention

This is a non-randomized and unblinded trial.

Interested participants will be first screened to determine study inclusion and exclusion criteria. Eligible participants will receive treatment in an outpatient setting and will be consecutively enrolled into treatment with one of the three study procedures: Procedure 1, Procedure 2, and Procedure 3.

Treatment will include following phases: 1) opioid withdrawal management, 2) initiation of naltrexone given orally followed by an injection of XR-naltrexone, 3) Outpatient relapse-prevention treatment, 4) administration of the second XR-naltrexone injection approximately 4 weeks after the first injection.

In addition to pharmacological treatment, all participants will receive a psychosocial intervention that will include elements of motivational interviewing and cognitive-behavioral relapse prevention therapy.

### **Sample Size**

Total enrollment goal is approximately 30 adult participants with OUD. We will enroll the first 10 participants in Procedure 1, the next 10 in Procedure 2, and the last 10 in Procedure 3.

## **Study Hypotheses**

Primary Hypothesis Procedure 1: Adjunctive treatment with buprenorphine 4 mg during the first 5 weeks of naltrexone maintenance will improve opioid abstinence and treatment retention, defined as receiving the second XR- NTX injection.

Primary Hypothesis Procedure 2: Providing buprenorphine 4 mg daily during gradual 9-day titration of oral naltrexone will improve tolerability and success of XR-NTX induction, defined as receiving the first XR-NTX injection.

Primary Hypothesis Procedure 3: Providing buprenorphine 4 mg daily during gradual 9-day titration of oral naltrexone and adjunctive treatment with buprenorphine 4 mg during the first 5 weeks of naltrexone maintenance will improve opioid abstinence and treatment retention, defined as receiving the second XR-NTX injection.

## **Study Outcome Measures**

### Procedure 1 and Procedure 3

Primary Outcome measure is the measure of XR-naltrexone initiation success defined as the receipt of two consecutive injections of XR-naltrexone.

### Procedure 2

Primary Outcome measure is the measure of detoxification and XR-naltrexone induction success defined as the receipt of the first injection of XR-naltrexone.

Safety of the proposed procedures will be evaluated using a structured instrument for obtaining treatment-emergent adverse effects.

Additional assessment will include measures of residual opioid withdrawal during treatment.

